10 STATISTICAL ANALYSIS

A statistical analysis will be carried out after the development of a basis for the collection of patient data, by protocol and in accordance with the principle of "intention to treat".

After identifying extreme data, a subsequent analysis will be carried out to assess the normality of the variables. All variables related to efficacy and safety will be analyzed for both treatment arms.

Categorical variables shall be expressed in percentages and number of observations. Continuous variables shall be expressed as mean and standard deviation or medians and interquartile ranges (25 – 75) and/or minimum and maximum. Relative risks of the estimated effect and its 95% confidence intervals shall be calculated and presented. For the comparison of categorical variables, the Chi-square test or the Fisher's test will be used, when necessary. For the comparison of the continuous variables, the Student's "t" test or Mann-Whiteney U test will be used for both simple and paired data, or other non-parametric tests, if necessary. Multivariate and survival analyses will be used to determine whether the association between the intervention and theprimary (or secondary) objective is free from confusion. Covariates in each model will be considered as those that in the univariate analysis show a value of p < 0.1

All analyses will be performed with hypothesis contrast of 2 tails and a significance level of 5%.

The statistical program used will be SPSS[®] 21.0.

Intermediate analyses are not planned except those indicated by the Safety Committee in order to safeguard the health of patients included in the study.

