In the work on the prophylaxis of delirium with antipsychotics, different tests have been used to identify patients at risk of developing delirium after surgery. One of the first was used by Kalisvaar to identify patients at risk of developing delirium after hip replacement surgery (21). Based on a scale of a study on delirium prophylaxis in patients undergoing general surgery, it used 4 items: visual deficit (measured with the Snellen test), APACHE II >16, Minimental Test > 24 and dehydration (BUN/creatinine ratio > 18). In this way, it classified patients with intermediate risk (if they had 1 or 2 items) or high risk if they had 3 or 4 (AUC 0.73). In 2014, Harasawa (22) used a new scale to predict the development of postoperative delirium in patients undergoing cerebrovascular surgery with a sensitivity of 71% and a specificity of 85.7%, area under the curve 0.844. It considers five variables: underlying disease (comorbidity), dehydration (nitrogen/creatinine index> 18), age >70 years, alterations in consciousness (Glasgow scale) and presence of depression-anxiety. Patients with a score greater than 12 were at increased risk of delirium. In that same year, in the published protocol of the HARPOON study (9), a multicenter trial that assesses the efficacy and safety of haloperidol prophylaxis in the prevention of delirium in elderly medical and surgical patients, they used three simple questions to identify patients at risk of developing delirium: about the patient's mental state (do they have memory problems?), on the degree of functionality (have you required help for your personal care in the last 24 hours?) and on the background (have you presented a state of transitory confusion during admissions or previous illnesses?). Each positive response scores as 1, and a score equal to or greater than 1 identifies a patient at risk. Except in this last study, the use of delirium risk predictor scales is complicated by the incorporation of other scales that hinder and slow down their realization. In this sense, in 2016 a delirium prediction scale was published to identify high-risk patients based on clinical data from the perioperative period: it is the Delphi method (23). The predictors used are: age, dependence for physical activities, alcoholism, hearing deficit, history of delirium, urgent surgery, open surgery, C-reactive protein value > 10 (mg/mL) and admission to critical care unit. A score equal to or greater than 7 classifies the patient as at high risk of developing delirium during the postoperative period. This predictor scale presents an area under the curve of 0.938 (95% CI: 0.91-0.97) and identifies the patient at high risk of developing delirium with a sensitivity of 80.8% and a specificity of 95.7%. It is simple, fast and easy to perform.

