- Baseline variables: demographic data, comorbidity, ASA classification, preoperative medication (sleep medication, antidepressants, opiates, corticosteroids), vital signs, previous baseline analysis with CRP, previous physical function (independent for daily life activities-Barthel index), previous cognitive function (assessed with MINIMental).
- Intraoperative variables: type of intervention and specialty, type of anaesthesia, intraoperative medication related in previous studies with delirium, duration of anaesthesia (min), anesthetic depth and regional cerebral oxygen saturation whenever possible, blood transfusion, degree of pain (by VAS scale) and postoperative medication related in previous studies with delirium and / or analgesic techniques used in this period.
- Complications not associated with delirium that require medical intervention (from grade II on the Clavien-Dindo scale ANNEX 5). They will be collected at the time of the patient's discharge and 28± 2 days after the start of treatment, in percentage. They must be registered in the corresponding section of the CRD, indicating the start date and severity according to the Clavien-Dindo scale. The list of complications to be collected is detailed in ANNEX 6 of this protocol. Inaddition, all those events that in the opinion of the researcher are relevant to the development of the study and patient safety should be collected.

5.2 STUDY DESIGN AND CONTROL METHOD.

Prospective low-intervention, non-commercial, balanced, randomized, double-blind clinical study (phase III).

5.3 PATIENT ASSIGNMENT AND IDENTIFICATION CODES.

Patientswill be identified with a code that will be generated with protocol code (QUEPRO) + correlative number, according to orrdin inclusion in the study. Example: The first patient included in the trial will receive the identification code QUEPRO-001; the second QUEPRO-002 and so on.

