6 PATIENT SELECTION AND WITHDRAWAL

6.1 INCLUSION CRITERIA.

Patients older than or equal to 65 years of age who are going to undergo major non-cardiac surgery and who have a score equal to or greater than 5 on the Delphi scale:

- Age: 70-79 years: 1 point; >80 years: 2 points.
- Physical activity: need for assistance, not self-sufficient: 2 pointss
- Alcoholism: 1 point.
- Hearing deficit: 1 point.
- History of delirium: 2 points.
- Urgent surgery: 1 point.
- Non-laparoscopic surgery: 2 points.
- Admission to Critical Units: 3 points.
- C-Reactive Protein (CRP) value > 10 mg/dL: 1 point.

6.2 EXCLUSION CRITERIA.

- × the lergia the quetiapine.
- × lactose intolerance.
- × patients with a score of less than 5 on the Delphi scale.
- × Diagnosis of delirium on admission.
- Cardiological diseases: QTc >460 msec in men, >470 msec in women, AMI or recent cardiac decompensation, AV block 2-3° or history of torsades de pointes arrhythmias or ventricular arrhythmias, bradycardia (<45 bpm).
- × hipopotasemia <3 mEq/CLK.
- × history of drug use.
- × Patients on antipsychotic or antidopaminergic treatment (chlorpromazine, clozapine, olanzapine, risperidone, haloperidol, quetiapine, paliperidone, amisulpride).
- × Parkinson's disease.
- × Minimental < 24.
- × vascular dementia or Levi's bodies.
- × Disorder of movements hipokinéticos.
- × History of neuroleptic malignant syndrome.
- × Central anticholinergic syndrome.
- × epilepsy.
- × patients weighing less than 50 or more than 200 kg.

× Patients participating in or having participated in a study of an investigational drug or device within four weeks prior to administration of the first dose of study treatment.

6.3 NUMBER OF PATIENTS.

Taking into account the current published literature, the estimated incidence of delirium in this type of population is 20-25%(2). We consider that a reduction in the absolute risk of delirium of 12% is clinically relevant , being similar to the reduction of absolute risk with non-pharmacological measures (10). Therefore, a sample size of 350 patients is estimated, with 175 subjects per treatment branch (significance level 95%, power 80%, expected losses of 5%).

6.4 EXPECTED CRITERIA FOR WITHDRAWAL OF STUDY SUBJECTS.

- 1. Voluntary patient abandonment: patients have the right to withdraw from the study at any time and for any reason, being able to express it personally or through their representative.
- 2. By medical criteria (safety and efficacy):

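### Section 10 names no primary analysis, and its only adjusted model is a confounding check with covariates picked at p < 0.1, so baseline predictors are not used for precision

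*Combined protocol and SAP*

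**What the plan says.** Section 5.1 defines the main variable as the proportion of patients diagnosed with delirium in the first 4 postoperative days. Section 10 sets out tests by type of variable and does not single out the main one. It states: "For the comparison of categorical variables, the Chi-square test or the Fisher's test will be used, when necessary". Relative risks with 95% confidence intervals are to be presented, and all tests are two-sided at 5%.

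The same paragraph of section 10 adds: "Multivariate and survival analyses will be used to determine whether the association between the intervention and theprimary (or secondary) objective is free from confusion". Covariates for each model are those with p < 0.1 in univariate analysis. There is no fixed list, no model family is named, and candidates are not limited to variables measured before randomisation.

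Several predictors are obtained before treatment. A Delphi score of 5 or more is an entry criterion (section 6.1). Section 5.1 lists among the baseline variables "previous physical function (independent for daily life activities-Barthel index), previous cognitive function (assessed with MINIMental", and Figure 1 places both at the selection visit. On the Delphi scale, section 3 reports: "This predictor scale presents an area under the curve of 0.938 (95% CI: 0.91-0.97".

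Section 6.3 sets the target: "We consider that a reduction in the absolute risk of delirium of 12% is clinically relevant". It takes a control incidence of 20-25%, 80% power and 5% losses, and arrives at 350 patients, 175 per arm.

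**The concern.** Two things are left open. First, the reader cannot tell which result decides the trial. The unadjusted test is the natural reading, but an adjusted model of the same objective stands beside it and neither is ranked.

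Second, the adjusted model is planned for the wrong purpose and in the wrong way. With 1:1 randomisation, confounding at baseline is dealt with by design; what baseline adjustment offers is precision. The p < 0.1 rule means the model cannot be written down until outcomes have been seen. Section 10 does not say what the univariate analysis is run against, but association with the outcome is the natural reading. Section 5.1 also collects intraoperative variables and postoperative medication, and nothing in section 10 keeps variables measured after treatment has started out of the candidate pool.

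At stake are a modest amount of power at no cost in patients, and protection against a choice between a crude result and a data-selected adjusted one.

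**Working it through.** **1. Reproduce the stated sample size.** Inputs from sections 6.3 and 10: two-sided alpha 0.05, power 80%, 12-point reduction, 5% losses. Take the top of the control range, 25% versus 13%, so the mean proportion is 0.19.

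n per arm = [1.96·√(2·0.19·0.81) + 0.842·√(0.25·0.75 + 0.13·0.87)]² / 0.12² = 166.6, so 167. Dividing by 0.95 gives 176 per arm, 352 in total, against the stated 350. The midpoint, 22.5% versus 10.5%, with continuity correction gives 166 and then 175 per arm, exactly 350. Either way, the size rests on an unadjusted comparison of proportions.

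**2. Power of the unadjusted test.** Evaluable patients: 175 × 0.95 = 166 per arm. The same formula solved for power gives 79.9% at 25% versus 13%, 84.1% at 22.5% versus 10.5%, and 88.7% at 20% versus 8%.

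**3. Power with a prespecified baseline score.** Simulation with 4,000 trials per case, 166 per arm, marginal risks held at 25% and 13%, and one normally distributed baseline score whose logistic slope is set to give the assumed AUC. The Monte Carlo standard error of each power is about √(0.8·0.2/4000) = 0.6 points. R² is the share of control-arm outcome variance that the score explains.

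| Assumed AUC in enrolled patients | R² | Chi-square | Standardised risk difference | Large-sample check |
|---|---|---|---|---|
| 0.60 | 0.024 | 80.9% | 82.0% | 81% |
| 0.65 | 0.054 | 80.6% | 82.0% | 82% |
| 0.70 | 0.098 | 79.9% | 83.2% | 84% |
| 0.75 | 0.156 | 80.7% | 86.1% | 86% |
| 0.80 | 0.230 | 79.8% | 88.3% | 89% |

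The last column is Φ(2.798/√(1 − R²) − 1.96), where 2.798 is the sum of normal quantiles that gives 79.9% power unadjusted. It agrees with the simulation. Repeat runs of 3,000 trials gave gains in the same ranges. With no treatment effect, the standardised test rejected in 5.0-5.2% of trials, and in 4.6-5.8% in a repeat run.

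**4. Choice of adjusted method.** Modified Poisson regression with robust variance gains less than standardisation. Chi-square to modified Poisson: 80.5% to 80.9% at AUC 0.65, 79.9% to 82.0% at 0.70, 80.7% to 85.2% at 0.75, and 79.8% to 86.1% at 0.80.

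**5. Room for covariates.** Expected events at 25% and 13%: 166 × (0.25 + 0.13) = 63. That supports only a short list.

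**The case against.** The strongest reply is that nothing here is an error. A chi-square or Fisher test with a relative risk is valid for a 1:1 randomised binary endpoint, it matches how the trial was sized, and it delivers the planned power. That stands. The point is a better method and a missing specification; it does not show bias.

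Several stronger readings are tempting, and the documents do not support them.

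- A reader might infer that the trial is underpowered or has no slack. The unadjusted test meets the 80% target at 25% versus 13% and exceeds it at lower control rates within the stated range.
- A reader might take the gain from the cited AUC of 0.938. That figure comes from the scale's source study. This trial enrols only scores of 5 or more and excludes MiniMental below 24, both of which narrow the spread of risk. No AUC among enrolled patients is given.
- A reader might argue that the planned confounding check must mislead, because an adjusted odds ratio moves away from the crude one even with balanced arms (0.448 to 0.394 at AUC 0.75). Section 10 names no logistic model and reports relative risks, which do not behave this way, so this is a risk only if odds ratios are used.
- A reader might think that only adjustment allows a comparison with the 12-point threshold. A crude risk difference with its interval would also do.

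It is also fair to say that the predictors are not perfectly assured. Section 7.2 allows MiniMental or 6 ICT for baseline cognition, and the numeric Delphi score has no row of its own in Figure 1. The score is implied by eligibility. These points affect the fix and do not remove the concern.

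**Conclusion.** The concern holds in a moderate form. Section 10 leaves the primary analysis unnamed, gives only a valid unadjusted test for the delirium endpoint, and confines adjustment to a confounding check with data-driven covariates.

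The size of the benefit depends on one quantity the documents do not give, the discrimination of the baseline predictors among enrolled patients. It is about 0-2 points of power at AUC 0.60-0.65, 3-4 at 0.70, 5-6 at 0.75 and 7-9 at 0.80. These figures assume 166 evaluable patients per arm, 25% versus 13%, and a single correctly modelled score chosen in advance. At the low end the precision gain is negligible. The case for naming and fixing the primary analysis does not depend on it.

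**What to change.** In section 10, before unblinding:

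- Name one primary analysis: a logistic model with arm and fixed covariates, standardised to give the marginal risk difference and relative risk, each with a 95% confidence interval.
- Fix the covariates as the Delphi score recorded at eligibility, before randomisation, plus baseline MiniMental. Require one cognitive instrument and remove the 6 ICT alternative for this purpose. Barthel is optional, since Delphi already scores physical dependence. Admit no variable measured after randomisation.
- Keep the chi-square or Fisher result as the supportive unadjusted analysis.
- Delete the p < 0.1 selection, and stop treating crude-versus-adjusted differences as a test for confounding.

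The cost is wording and no extra patients. The Delphi score must be captured as a number in the data collection notebook. The plan needs a simple rule for missing covariates and one for non-convergence, such as falling back on the unadjusted result. With about 63 expected events, the covariate list must stay short. It should also be confirmed that SPSS 21.0, the program section 10 names, can produce the standardised estimates and their intervals; if not, another program should be named.

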4 HYPOTHESES AND OBJECTIVES

Hypothesis: The prophylactic administration of an antipsychotic with fewer side effects, such as quetiapine, in patients identified with a validated scale decreases the incidence of delirium during the postoperative period compared to placebo administration.

The main objective of the study is to determine the incidence of postoperative delirium in patients at risk, over 65 years of age, treated early with prophylactic quetiapine compared to those treated with placebo.

The secondary objectives are:

- eassess the safety and tolerability of the medication applied.
- cCompare the efficacy of medication versus placebo in relation to:
 - the length of hospital stay.
 - perceived quality of life at 28±2 days from the start (1st dose) of quetiapine treatment.
 - all-cause mortality at discharge and 28±2 days from initiation (1st dose) of quetiapine therapy.
- In cases where delirium develops, know:
 - Time of appearance.
 - the duration and severity of the same.
 - total treatment with other antipsychotics.

5 CLINICAL TRIAL DESIGN.

5.1 . DESCRIPTION OF VARIABLES

The main variable is the proportion of patients diagnosed with delirium (number of delirium cases/total number of patients) in the first 4 postoperative days. We will use a validated scale based on the DSM-IV definition of delirium, CAM: *Confusion Assessment Method* scale (17,24-27).

The secondary variables are:

- 1. Number of days from the start of treatment to the onset of delirium, if it appears.
- 2. duration of delirium, in days.
- 3. severity of theirium measured with validated scale (DRS-R-98).
- 4. D Total osis (mg) haloperidol or another antipsychotic tocontrol the symptoms of delirium.
- 5. Security Costs:
 - Sedation degree: using RASS scale.
 - QTc prolongation: increase in mseg in the control ECG.
 - presence or absence of extrapyramidal symptoms (tremor, involuntary movements, rigidity).
- 6. Days ofhospital stay of the surgical intervention.
- 7. perceived quality of life (through validated questionnaire SF36 or SF 12) 28±2 days after initiation of treatment.
- 8. mortality from all causes at discharge and 28±2 days after initiation of treatment.

Additional variables that will also be collected:

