8 N-ASSESSMENTOF EFFECTIVENESS

8.1 EFFICACY VARIABLES.

The efficacy of the treatment is given by the main variable: incidence of delirium during the postoperative period in the first 4 days in both intervention groups.

The secondary variables will be collected: number of days free of delirium, duration and severity of delirium if it finally develops; hospital stay, adverse effects, mortality at discharge and 28 ± 2 days, perceived quality of life at 28 ± 2 days.

8.2 EVALUATION METHODS.

To obtain the main variable we will use the CAM scale (Confusion Assessment Method) as a method of diagnosis of the appearance of delirium. It is a scale based on the DSM IV definition of delirium (29) and with demonstrated internal and external validity for surgical patients (17,24-27). It consists of an interview of the clinician consisting of six items: two addressed to the closest caregiver (family member or nursing technician) with which information is obtained on the beginning of the picture and the presence of fluctuations. The remaining four items are to ask the patient, to determine their cognitive impairment that evaluates attention, thinking and consciousness. In the second part of the instrument, the clinician answers a questionnaire of 4 questions (yes / no), based on the evaluation made. The diagnosis of delirium is established around the presence of its two fundamental criteria (abrupt onset with fluctuations of symptoms and loss of attention) and one of the two secondary criteria (disorganized thinking and altered level of consciousness). We will use the same scale to rule out the presence of delirium in the initial assessment of the patient and to determine the duration of the picture during the follow-up period. The assessment of the response will be carried out daily in both study groups, during the first 4 days of admission or until the patient's discharge.

We will use the RASS scale (Richmond Agitation sedation scale) to assess the degree of sedation or agitation presented by the patient. It is a 10-point scale, very intuitive in its description since the positive values indicate agitation and the negative values are used to quantify sedation, in such a way that level 0 corresponds to a calm and awake patient, level 4

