to the situation of maximum agitation and level -5 to the highest depression of the level of consciousness. It also has a good correlation with the appearance of delirium when the presence or absence of attention is detected (30). It will be administered prior to CAM during the follow-up period, if -4/-5 values are obtained, it will be repeated again after two hours until it decreases to -3 values onwards. In case of development of delirium, daily follow-up (through CAM and RASS scales) will be carried out until resolution of the patient's condition or discharge and the drugs used for symptom control and the necessary doses will be recorded in the CRD.

The severity of delirium developed will be determined by the DRS-R-98 scale (31,32). Itis a scale of 16 items scored by the clinician with two sections (severity and diagnosis) and a score sheet. The 13 items in the severity section can be scored separately from the 3 items in the diagnostic section. The severity section functions as a standalone scale for repeated measurements during an episode of delirium. All items are accompanied by descriptions that serve as a guide for scoring along a continuum that moves between normality and severe involvement, scoring between 0 and 3. All available sources of information can be used for patient assessment: family, visitors, hospital staff, even the roommate can contribute more information. Some items are scored based on test and medical history, while others incorporate standardized questions (e.g., language and cognitive items). The items assessed are: circadian rhythm alteration, alterations in perception and hallucinations, delusions, affective lability, language alterations, alterations in the course of thought, agitation or motor slowdown, orientation, attention, short and long-term memory, visuospatial capacity. Only the severity section of the scale will be administered once a day for as long as you develop delirium.

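### The p < 0.1 covariate rule has no pre-dose limit, so post-dose variables such as RASS can enter the adjusted models and bias the treatment effect

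*Combined protocol and SAP*

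**What the plan says.** Section 10 gives the adjusted models a purpose: "Multivariate and survival analyses will be used to determine whether the association between the intervention" and the primary or secondary objective is free of confounding. The selection rule follows: "Covariates in each model will be considered as those that in the univariate analysis show a value of p < 0.1". There is no candidate list and no timing limit. The same section plans a chi-square or Fisher test for categorical variables, and relative risks with 95% confidence intervals. It does not rank these against the adjusted models.

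On RASS and the other possible candidates:

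- Section 5.1 lists it among the safety variables ("Sedation degree: using RASS scale"), apart from the additional variables to be collected.
- Section 7.1 times the first capsule at 60 minutes after arrival in the resuscitation unit. Figure 1 in section 7.2 has no RASS at pre-selection or selection; it starts at postoperative visit 1. Section 8.2 agrees: "It will be administered prior to CAM during the follow-up period".
- Section 3 expects quetiapine to sedate, and section 5.4 lists drowsiness among its most frequent reactions.
- Section 8.2 makes altered level of consciousness one of the CAM criteria, and item 4 of the CAM annex includes sleepiness. Section 8.2 also says of RASS: "It also has a good correlation with the appearance of delirium when the presence or absence of attention is detected".
- The additional variables in section 5.1 do not supply a timing limit. The intraoperative group there includes "postoperative medication related in previous studies with delirium", and complications up to day 28 follow as a further group.

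**The concern.** In a randomised trial, covariates measured before treatment can be adjusted for safely. A variable that the treatment changes cannot, if it is also tied to the outcome. Adjusting for it removes no confounding; it creates bias.

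RASS fits that description on the protocol's own account. Its link to delirium also makes it likely to pass a p < 0.1 screen. If delirium mostly lowers RASS (hypoactive), a low score on quetiapine is partly explained by the drug, and the adjusted model exaggerates the benefit. If delirium mostly raises RASS (hyperactive), the adjusted model masks the benefit.

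What is at stake is the model meant to show that the effect is not due to confounding. It could contradict a sound unadjusted result, or make that result look stronger than it is. With no ranking of the two analyses, the plan does not say how such a conflict would be settled.

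**Working it through.** **1. Plan's figures.** Section 6.3 gives control incidence 20-25%, absolute reduction 12 points, two-sided 5%, power 80%, 5% losses and 175 per arm. With n per arm = [1.96·√(2·p̄·(1−p̄)) + 0.842·√(p1(1−p1) + p2(1−p2))]² / (p1−p2)², p1 = 0.25, p2 = 0.13 and p̄ = 0.19:

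(1.96·√0.3078 + 0.842·√0.3006)² / 0.0144 gives 167. Then 167/0.95 gives 176 per arm, 352 in total, close to the stated 350. No stated figure is in dispute. The simulations use 175 × 0.95 ≈ 166 evaluable per arm.

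**2. Simulation, ordinal RASS (all shifts assumed).** Scores are rounded and held to −5 to +4, with latent SD 1 point and within-patient correlation 0.5. The drug lowers RASS on days 1-3. Delirium onset is uniform over days 1-4 and moves RASS by 1 point, down if hypoactive and up if hyperactive. The covariate is the 4-day mean or the lowest value, entered if its univariate association with delirium has p < 0.1. The treatment test is a logistic Wald test. There are 2,500 trials per setting, so the Monte Carlo standard error at 5% is √(0.05 × 0.95/2500) = 0.4 points.

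Null rejection, 25% delirium in both arms (4-day mean / lowest value):

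| Hypoactive share | Drug −0.25 point | Drug −0.5 point |
|---|---|---|
| 75% | 5.8% / 5.9% | 8.5% / 10.0% |
| 50% | 5.5% / 5.4% | 4.8% / 4.7% |
| 25% | 6.1% / 5.3% | 9.2% / 5.5% |
| 100% (extreme) | 10.0% / 9.5% | 24.8% / 22.6% |
| 0% (extreme) | 10.1% / 7.0% | 26.2% / 14.1% |

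A repeat run of the 75%, −0.5 case (4-day mean) gave 9.6%, with RASS passing the screen in 86% of trials. Adding the section 7.3 rule that study medication stops when delirium develops changed little.

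**3. True effect 25% vs 13%, drug −0.5 point.** The unadjusted log-odds ratio is −0.81 (odds ratio e^−0.81 = 0.44), with power about 80%.

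| Hypoactive share | Adjusted log-odds ratio (mean / lowest) | Odds ratio | Rejection |
|---|---|---|---|
| 75% | −0.94 / −1.00 | 0.39 / 0.37 | 88.9% / 91.4% |
| 25% | −0.64 / −0.73 | 0.53 / 0.48 | 56.2% / 69.6% |

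**4. A different data model.** Here sedation is binary, assumed at 20% on placebo and 35% or 50% on quetiapine, and shares an unmeasured frailty with delirium (350 patients, 1,000 runs per setting, no drug effect on delirium). Null rejection is 4.4-4.5% with weak sharing, 7-10% with moderate sharing and 9-21% with strong sharing. The unadjusted model rejects 3.7-5.2%. The pattern is the same: negligible to material, depending on the assumed association.

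**5. Pre-dose candidates only.** With the same p < 0.1 screen applied to 3 prognostic and 10 noise variables, all measured before dosing, null rejection is 4.6-5.1% and power 79-86%. The timing limit alone removes the problem.

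**The case against.** The strongest reply is that RASS entry is inferred. Section 5.1 treats RASS as a safety outcome, section 10 never names it as a covariate, and a model meant to rule out confounding should not adjust for a consequence of treatment. RASS is also measured daily, and no single summary is defined; the 4-day mean and lowest value are choices made for the simulation. This stands as a limit. It does not close the gap, because the written rule is the p value and nothing excludes RASS.

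The expected sedation is also uncertain. Section 3 reports few side effects, mainly drowsiness, without significant differences, and describes prophylactic doses as lower than those used for treatment. The drowsiness frequency in section 5.4 comes from the general product information. No passage gives a RASS shift in this setting, so the small-shift results must be given equal prominence.

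A reader might infer three stronger points that the documents do not support:

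- *The plan will adjust for RASS.* It does not say so.
- *The type I error of the adjusted model is 14-26% or more.* Figures of that size need all delirium to be of one motor type, or comparably strong assumptions elsewhere.
- *VAS, analgesia and complications would cause the same bias.* The rule could admit them, but no passage shows that quetiapine changes them.

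**Conclusion.** The concern holds as a defect in the selection rule, with RASS as its clearest example. Section 10 can, read literally, put a post-dose variable into a model whose purpose is to rule out confounding.

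The size rests wholly on assumed shifts:

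- Inflation of null rejection is negligible with a 0.25-point drug shift and mixed motor types, or with a 50:50 mix.
- Null rejection is about 5-10% with a 0.5-point shift in a mixed population.
- Under that 0.5-point shift, power falls to about 56-70% if delirium is mostly hyperactive, and the benefit is overstated if it is mostly hypoactive.

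A reader might conclude that the trial's main result is compromised. It is not: the unadjusted chi-square or Fisher test and the relative risk do not use the rule. Nor do the documents formally name that comparison as primary. Section 8.1 ("The efficacy of the treatment is given by the main variable") and section 6.3 fix the main variable and the sample size but name no test. Treating the adjusted model as supportive is a reasonable reading of its purpose, which the plan should state. The change should be made because the written rule can do worse than a simple replacement that costs almost nothing.

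**What to change.** Preferred: in section 10, replace the p < 0.1 screen with a short covariate set fixed before unblinding and measured before the first capsule in all patients. Age and the Delphi total as scored at selection would be one example. Use baseline cognition only if one instrument is used for everyone, since section 7.2 allows an alternative to MiniMental.

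At minimum, add two statements:

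1. Candidates are limited to items recorded before the first capsule, judged item by item by time of measurement and not by the group heading in section 5.1. Intraoperative drugs, and analgesia given before the first capsule, may enter. RASS, daily VAS, medication or analgesia given after the first capsule, and complications may not.
2. The adjusted model supports the unadjusted comparison.

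The item-level wording matters because section 5.1 places pain scores and postoperative medication in the intraoperative group, and section 7.2 lists analgesia and VAS on recovery-unit admission among the intraoperative items.

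Cost: one or two sentences and, for the preferred version, choosing the covariates now. The sample size does not change.
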